Subjects with prolactinomas who are resistant to dopamine agonist therapy who manifest continued tumor size growth while on a dopamine agonist, unless intolerant of adequate doses of a dopamine agonist.

Subjects with malignant pituitary tumors will be eligible for the malignant pituitary tumor arm of the study regardless of existing visual deficits.

Exclusion criteria: Children will be excluded. If subjects have preexisting visual field deficits, they will be monitored on more frequent basis. Patients will also be excluded if they have left ventricular ejection fraction less than 50 %, moderate to severe hepatic impairment (see below for specifics), active hepatitis, HIV positivity, concurrent cancers, life expectancy less than one year, and pregnancy. Pregnant patients will be excluded. Childbearing age women will be required to use

contraception. Patients who become pregnant during the study should discontinue the study immediately.

Withdrawal of Subjects:

Monitoring for adverse effects: Prior to initiating therapy, patients will undergo an echocardiogram and ECG to evaluate the ejection fraction, and the echocardiogram will be repeated every 8 weeks (Visit 3, 5, and 7) and on visit 8. Patients will also undergo ophthalmic testing at visits 1, 4, and 7. Patients with pre-existing stable visual field compromise prior to enrollment will undergo visual field testing at visits 1, 2, and 3, and if stable, then they will proceed with visual field testing every three months for the duration of the study. Patients will be evaluated for adverse effects monthly with physical examinations, chemistry and hematology panels, and ECGs. Adverse events will be graded by the NCI-CTC and include: anorexia, decreased ejection fraction, interstitial lung disease/pneumonitis, diarrhea, nausea, vomiting, hepatotoxicity, rash, and fatigue. Lapatinib will be discontinued in those who developed decreased ejection fraction, who develop pulmonary symptoms, retinal toxicity, worsening of visual fields, and those with toxicity greater than or equal to Grade 2 on the NCI-CTC. [name], from Oncology department at Cedars-Sinai Medical Center, will assist us in monitoring patients for adverse events.

If at any time a patient demonstrates compromise of his visual fields, dilated retinal exam or tumor growth on MRI, he will be withdrawn from the study and referred for surgery.

Section 6.0 Treatment of Subjects

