MRI—this will be waived if subjects had an MRI performed at their outside hospital within 3 months of the 1st study visit and if subjects provide a CD of the images for review by our neuroradiologist to determine if of sufficient quality for a baseline study.

While on the drug, visits will occur once a month to monitor for adverse effects. Patients' visits may not deviate more than 7 days from the 30-day mark between each visit.

Visit 2: time 1 month on drug

Physical exam and history

Will draw CBC with differential, BMP, LFTs (15 cc blood)

For those with prolactinomas, will also check PRL.

For those with acromegaly from malignant tumors, will GH levels on 2 hour OGTT

For those with ACTH secreting malignant tumors, will check 24 hour urinary free cortisol

Do ECG

Urine Pregnancy Test

Those with pre-existing visual field compromise, visual field testing

Visit 3: time 2 months on drug

Physical exam and history

Will draw CBC with differential, BMP, LFTs (15 cc blood)

For those with prolactinomas, will also check PRL.

For those with acromegaly from malignant tumors, will check GH levels on 2 hour OGTT

For those with ACTH secreting malignant tumors, will check 24 hour urinary free cortisol

Those with pre-existing visual field compromise, visual field testing

Do ECG, echocardiogram

Urine Pregnancy Test

Visit 4: time of 3 months on drug

Physical exam and history

Will draw CBC with differential, BMP, LFTs (15 cc blood)

For those with prolactinomas, will also check PRL.

For those with acromegaly from malignant tumors, will check GH levels on 2 hour OGTT

For those with ACTH secreting malignant tumors, will check 24 hour urinary free cortisol

Pituitary hormones as well—TSH, thyroid panel, free T4, 8 am cortisol (if indicated), IGF-1, LH, FSH, testosterone (15 cc blood)

Tubes for lab for EGFR, her2 levels (10 cc blood)

Do ECG
Visual field test
Dilated retinal exam
Color Vision test
Do MRI of pituitary with and without IV gadolinium
Urine Pregnancy Test

Visit 5: time of 4 months on drug
Physical exam and history
Will draw CBC with differential, BMP, LFTs (15 cc blood)
For those with prolactinomas, will also check PRL.
For those with acromegaly from malignant tumors, will check GH levels on 2 hour OGTT
For those with ACTH secreting malignant tumors, will check 24 hour urinary free cortisol
Do ECG, echocardiogram
Urine Pregnancy Test

Visit 6: time of 5 months on drug
Physical exam and history

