Will draw CBC with differential, BMP, LFTs (15 cc blood)
For those with prolactinomas, will also check PRL.
For those with acromegaly from malignant tumors, will check GH levels on 2 hour OGTT
For those with ACTH secreting malignant tumors, will check 24 hour urinary free cortisol
Do ECG
Urine Pregnancy Test
Those with pre-existing visual field compromise, visual field testing

Visit 7: time of 6 months on drug
Physical exam and history
Will draw CBC with differential, BMP, LFTs (15 cc blood)
For those with acromegaly from malignant tumors, will check GH levels on 2 hour OGTT
For those with ACTH secreting malignant tumors, will check 24 hour urinary free cortisol
Pituitary hormones as well—PRL, TSH, thyroid panel, free T4, 8 am cortisol (if indicated), IGF-1, LH, FSH, total and free testosterone for males (15 cc blood)
Tubes for lab for EGFR, her2 levels (10 cc blood)
Do ECG, Echocardiogram
Check visual fields
Dilated retinal exam
Visual acuity check
Ocular pressure check
Color Vision test
Do MRI of pituitary with and without IV gadolinium
Urine Pregnancy Test

Visit 8: time of 1 mo off drug
Physical exam and history
Will draw CBC with differential, BMP, LFTs (15 cc blood)
For those with prolactinomas, will also check PRL.
For those with acromegaly from malignant tumors, will check GH levels on 2 hour OGTT
For those with ACTH secreting malignant tumors, will check 24 hour urinary free cortisol
Draw tubes for EGFR, Her2 levels (10 cc blood)
Do ECG, Echocardiogram

Urine Pregnancy Test

Note: Study visits may be conducted over 2 days to allow for sufficient time to complete the procedures, scheduling availability, and patient preference.

Study procedure flowsheet:

(See following page)

Procedure	Baseline Visit	Visit #2 (+30 days)	Visit #3 (+60 days)	Visit #4 (+90 days)	Visit #5 (+120 days)	Visit #6 (+150 days)	Visit #7 (+180 days)	Visit #8** (+210 days)
Laboratory Blood Tests (may include levels of hormones, cholesterol, CBC, and metabolic panel)	X	X	X	X	X	X	X	X
MRI of the Pituitary	X^^			X			X	
Echocardiogram	X		X		X		X	X
Electrocardiogram (ECG)	X	X	X	X	X	X	X	X
Visual Field Test	X	X^	X^	X		X^	X	
History and Physical	X	X	X	X	X	X	X	X
Informed Consent	X							
Color Vision Test	X			X			X	
Ocular Pressure Check	X						X	
Visual Acuity	X						X	
Dilated Retinal Exam	X			X			X	
Hormonal profile	X	X	X	X	X	X	X	X
Oral Glucose Tolerance Test (OGTT) (malignant arm)	X*	X*	X*	X*	X*	X*	X*	X*

24-hour Urinary Free Cortisol (malignant arm)	X+							

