Pregnancy Test for pre-menopausal women	X	X	X	X	X	X	X	X

^ Only for subjects with visual field deficits

^^ will be waived if subjects had MRI at outside hospital within 3 months of baseline visit

* Only for subjects with acromegaly from malignant tumors

+Only for subjects with ACTH secreting adenomas from malignant tumors

**Visit 8 is only required if stopping Lapatinib at visit 7. Patients continuing on Lapatinib after visit 7 will be followed by their physician as clinically appropriate.

Section 7.0 Assessment of Efficacy

a. Primary outcome variable.

Primary outcome in nonfunctioning pituitary adenomas: 40% reduction in tumor size in any dimension. Tumor size and volume will be calculated using Open Source OsiriX® Imaging Software for MacOS. MRIs will be performed at baseline and at 3 and 6 months All MRIs will be centrally read by the dedicated pituitary radiologist at CSMC.

Primary outcome in prolactinomas: 40% reduction in tumor size in any dimension.

Primary outcome in malignant pituitary tumors: Progression free survival

b. Secondary outcome variables.

Secondary outcomes in prolactinomas:

(a) achievement of 50% reduction of PRL levels (b) PRL normalization (c) percent reduction in PRL levels (d) percent reduction in tumor volume. Tumor volume will be calculated using Open Source OsiriX® Imaging Software for MacOS. (e) correlation of tumor size and PRL reduction (f) clinical predictors of TKI response, including age, gender, duration of disease, dose and duration of dopamine agonist therapy, baseline PRL, and baseline tumor size.

Secondary outcomes in malignant pituitary tumors: partial response, complete response, mortality, 24 hour urine free cortisol levels for Cushing carcinomas, IGF-1 levels for acromegaly carcinomas

We will correlate ErbB receptor expression with the subjects' clinical response to the study drug. This will be performed through immunohistochemistry staining of pituitary tumor slides from surgery.

Section 8.0 Assessment of Safety

1. *Monitoring for adverse effects (further detailed below):* Data has been collected on over 12000 subjects on combination therapy of lapatinib and other chemotherapies, and over 4000 subjects have been treated with lapatinib monotherapy, with 2347 of those specifically in breast cancer. With monotherapy, majority of AEs were Grade 1 or 2 in severity. The incidence of Grade 3 and Grade 4 events was 21% in those

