Record the appearance or worsening of clinical symptoms of hepatitis, or hypersensitivity, fatigue, decreased appetite, nausea, vomiting, abdominal pain, jaundice, fever, or rash as relevant on an AE report form;

Record use of concomitant medications, acetaminophen, herbal remedies, other over the counter medications, or putative hepatotoxins, on the concomitant medications report form;

Record alcohol use on the liver event alcohol intake case report form.

Refer to Appendix 3 for a liver safety algorithm detailing stopping and follow up criteria.

Safety

Add frequency of LFTs to Safety Assessment section and Time & Events Table as applicable:

- During treatment phase: every 4 - 6 weeks (to best fit protocol schedule) for duration of concurrent chemotherapy administration or for first 6 months, then

every 8 – 12 weeks (or more frequently, if clinically indicated) for remaining on treatment period

- During post-treatment phase: continue to monitor any liver chemistry abnormalities noted during treatment or within 30 days after last dose of investigational product until values return to normal or baseline (this language should be in protocols already)

In the Safety Assessment section, make a reference to section containing the Liver Chemistry Stopping and Follow up Criteria.

In the Laboratory Assessment section, mention that bilirubin fractionation is recommended if total bilirubin $>2 \times$ ULN when testing is available.

[figure not shown]
Hepatobiliary events have been seen in subjects taking lapatinib and other tyrosine kinase inhibitors. As a precaution, the following will be reported as an SAE:

- ALT $>3 \times$ ULN and total bilirubin $>2.0 \times$ ULN ($>35\%$ direct; bilirubin fractionation required).

NOTE: bilirubin fractionation should be performed if testing is available. If testing is unavailable and a subject meets the criterion of total bilirubin $>2.0 \times$ ULN, then the event should still be reported as an SAE.

Other hepatic events should be documented as an AE or an SAE as appropriate.

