The Investigator, or a responsible party designated by the investigator, must maintain a careful record of the inventory and disposition of all agents received from Novartis.

REGULATORY AND REPORTING REQUIREMENTS

It is the responsibility of the investigator to document all adverse events which occur during the investigation. An adverse event is any untoward medical occurrence in a patient or clinical investigation subject, temporally associated with the use of the medicinal product, whether or not considered related to the medicinal product. *An AE can therefore be any unfavorable and unintended sign (including an abnormal laboratory finding), symptom, or disease (new or exacerbated) temporally associated with the use of a medicinal product.* Anticipated day-to-day fluctuations of the disease under study that do not represent a clinically significant exacerbation or worsening need not be considered an adverse event.

RECOMMENDED ELEMENTS OF A SCIENTIFIC PROTOCOL
(Noted sections should only be included as applicable to your research)

32

All adverse events occurring from the first dose of investigational product until five days after the last dose must be recorded **REGARDLESS OF WHETHER OR NOT THEY ARE CONSIDERED DRUG RELATED**. In addition, any SAEs which occur as a result of protocol specific diagnostic procedures or interventions must also be reported.

It is the responsibility of the IND holder to comply with IND safety reporting as set forth in the Code of Federal Regulations, Section 312.32.

Assessment of Causality

Every effort should be made by the investigator to explain each adverse event and assess its relationship, if any, to study drug treatment. Causality should be assessed using the following categories: no (not related), or yes (reasonable possibility).

The degree of certainty with which an adverse experience is attributed to drug treatment (or alternative causes, e.g. natural history of the underlying diseases, concomitant therapy, etc.) will be determined by how well the experience can be understood in terms of the following:

- Known pharmacology of the drug
- Reaction of similar nature being previously observed with this drug or class of drug
- The event having often been reported in literature for similar drugs as drug related (e.g. skin rashes, blood dyscrasia)
- The event being related by time to drug administration terminating with drug withdrawal (dechallenge) or reproduced on rechallenge.

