Pregnancy	2 Weeks	Pregnancy Notification Form	2 Weeks	Pregnancy Follow up Form
Liver chemistry abnormalities:				
ALT $>3 \times \text{ULN}$ and bilirubin ^a $>2 \times \text{ULN}$ (35% direct)	24 hours	CRF	24 hours	CRF

- a. bilirubin fractionation should be performed if testing is available. If testing is unavailable and a subject meets the criterion of total bilirubin $>2.0 \times \text{ULN}$, then the event should still be promptly reported as defined.

Reporting Serious Adverse Events

Any serious adverse events which occur during the clinical study or within 30 days of receiving the last dose of study medication, whether or not related to the study drug, must be reported by the investigator. In addition, any SAEs which occur as a result of protocol specific diagnostic procedures or interventions must also be reported.

The principal investigator has the obligation to report all serious adverse events to the FDA, IRB, and Novartis Pharmaceuticals Drug Safety and Epidemiology Department (DS&E) (***For patients taking Lapatinib / Novartis drugs***).

All events reported to the FDA by the investigator are to be filed utilizing the Form FDA 3500A (MedWatch Form).

To ensure patient safety, every SAE, regardless of suspected causality, occurring

- after the patient has provided informed consent and until at least 30 days after the patient has stopped study treatment/participation
- after protocol-specified procedures begin (e.g., placebo run-in, washout period, double-blind treatment, etc.) and 30 days after the patient has stopped study treatment

RECOMMENDED ELEMENTS OF A SCIENTIFIC PROTOCOL
(Noted sections should only be included as applicable to your research)

35

- after the start of any period in which the study protocol interferes with the standard medical treatment given to a patient (e.g., treatment withdrawal during washout period, change in treatment to a fixed dose of concomitant medication) and until 30 days after the patient has stopped study treatment

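### The five-day limit on recording adverse events conflicts with the one-month off-drug visit, the 30-day windows and the protocol's own undated recording duties

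*Combined protocol and SAP*

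**What the plan says.** The general recording rule is in Section 8.0, Regulatory and Reporting Requirements: "All adverse events occurring from the first dose of investigational product until five days after the last dose must be recorded", whether or not the event is thought to be drug related. No other sentence puts a day limit on recording adverse events in general.

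Other rules reach further:

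- The same subsection opens with a duty that has no day limit: "It is the responsibility of the investigator to document all adverse events which occur during the investigation". The definition of an adverse event that follows asks only for a temporal association with the product.
- Under Definition of Serious Adverse Events, abnormal laboratory values and other abnormal assessments that the investigator judges clinically significant are to be recorded as adverse events or serious adverse events if they meet the definition. No time limit is given.
- Reporting Serious Adverse Events covers "Any serious adverse events which occur during the clinical study or within 30 days of receiving the last dose of study medication".
- The Safety subsection has liver chemistry abnormalities monitored if they are "noted during treatment or within 30 days after last dose of investigational product".
- Section 6.0 schedules "Visit 8: time of 1 mo off drug", with history and examination, blood counts, chemistry, liver tests, ECG and echocardiogram. Section 5.0 places the echocardiogram at this visit under monitoring for adverse effects: "the echocardiogram will be repeated every 8 weeks (Visit 3, 5, and 7) and on visit 8".
- The flowsheet footnote limits who attends: "Visit 8 is only required if stopping Lapatinib at visit 7".

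**The concern.** Section 9.0 describes the study as a trial of safety and activity. It schedules a visit one month off drug to look for toxicity, yet the one explicit general window for recording adverse events has closed well before that visit. Under the five-day sentence, a new non-serious event starting between day 6 and Visit 8 carries no recording requirement. Other sentences in Section 8.0 point the other way.

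At stake is whether late non-serious events are captured consistently. Section 4.0 names three sites. One site could follow the five-day sentence and another the general duty, so the count of late events would partly reflect which sentence each site read. An event that is not recorded as an adverse event also has no required causality assessment. A symptom reported only in the history has no separate measured endpoint to fall back on.

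**Working it through.** **Inputs**

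- General adverse-event window: last dose + 5 days (Section 8.0, Regulatory and Reporting Requirements).
- Serious-event and liver-chemistry windows: last dose + 30 days (Section 8.0).
- Visit 7 at +180 days and Visit 8 at +210 days (Section 6.0 flowsheet).
- Visit tolerance: "Patients' visits may not deviate more than 7 days from the 30-day mark between each visit" (Section 6.0). This is stated for the monthly on-drug visits; applying it to Visit 8 is an assumption.
- Last dose taken at Visit 7, the case for which the footnote requires Visit 8.

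**Step 1. Reproduce the plan's own timing.** 210 − 180 = 30 days off drug, which agrees with the stated one month.

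**Step 2. Time between the end of the five-day window and Visit 8.** 30 − 5 = 25 days, and 25/30 = 83% of the off-drug interval.

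**Step 3. Range if the 7-day tolerance applies.** Visit 8 falls between 30 − 7 = 23 and 30 + 7 = 37 days off drug. The gap is then 23 − 5 = 18 to 37 − 5 = 32 days.

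**Step 4. What a plain 30-day window would do.** For a Visit 8 on schedule the gap is 30 − 30 = 0 days. For a visit at the late limit, 37 − 30 = 7 days would still lie outside it.

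**Step 5. Apply the rules to each kind of event in a patient stopping at Visit 7.**

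| Event | Five-day sentence | Other rules | Result |
|---|---|---|---|
| Began by day 5, found at Visit 8 | Must be recorded | – | Covered |
| Already recorded | – | Followed until it subsides or stabilises | Covered |
| Serious, up to day 30, including Grade 4 laboratory values and the specified cardiac and hepatobiliary events | – | Reported | Covered |
| Liver chemistry abnormality, up to day 30 | – | Monitored | Covered |
| Non-serious, non-hepatic test abnormality starting after day 5 | Not required | Required by the undated rule if judged clinically significant | Conflict |
| Non-serious symptom starting after day 5, e.g. rash | Not required | Required by the general duty | Conflict |
| Non-serious, non-hepatic test change first seen at Visit 8 | Depends on an unknown onset | Required by the undated rule if judged clinically significant | Conflict |

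The last row arises because no assessment is scheduled between Visits 7 and 8. An echocardiogram, ECG or blood result that was normal at Visit 7 and abnormal at Visit 8 changed at some point in a 30-day interval, and nothing in the schedule says whether that was before or after day 5.

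**The case against.** A reader might infer that every non-serious event found at Visit 8 is lost to the safety data, and that the DSMB's counts and the adverse-event tables will omit it. The documents do not support that, for five reasons.

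1. The window is set by when the event occurs and not by when it is found.
2. The general duty to document events, and the undated rule for clinically significant abnormal assessments, both extend past day 5. The second reaches an ECG change or a fall in ejection fraction below the serious-event threshold, provided the investigator judges it clinically significant.
3. The five-day sentence says what must be recorded. It does not say that later events are excluded.
4. Visit 8 test results are scheduled study data whether or not an adverse event is coded.
5. Section 9.0 specifies no adverse-event tables, and Section 8.0 says only that a DSMB will monitor safety, so a claim about what either would omit is inference.

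It can also be said that five days was chosen deliberately, since the Pregnancy subsection uses the same interval, and that 83% is a share of calendar days, not of events. Both remarks are fair. But the documents give no reason for five days as the limit on recording adverse events.

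All of this narrows the point without removing it. The undated duties do not override the five-day sentence; they contradict it, and nothing says which governs. Doubt about onset also does not help, because it leaves the decision on a Visit 8 finding to each site. The limit on who attends Visit 8 does not help either: a patient who continues lapatinib has not yet had a last dose, so the off-drug window has not opened.

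**Conclusion.** The point holds as an internal inconsistency with a practical consequence, not as a proven exclusion of events. The only explicit general recording window ends 25 days before an on-schedule Visit 8, or 18 to 32 days before it if the on-drug visit tolerance also applies there. What is left without a clear rule is narrow: new non-serious events, other than liver chemistry abnormalities, with onset after day 5 or with an onset that cannot be dated. Examples are a rash, or a non-hepatic laboratory change below Grade 4.

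The number of such events cannot be estimated, because the documents give no rate of new onset after stopping lapatinib. The result assumes that the last dose is taken at Visit 7. It affects the completeness and consistency of the safety data only; the efficacy outcomes and the sample size are untouched.

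**What to change.** Replace the five-day sentence with one adverse-event recording window: from the first dose to 30 days after the last dose or to Visit 8, whichever is later. Make the general duty to document events and the rule for clinically significant abnormal assessments refer to that same window. The words on whichever is later are needed because a 30-day limit alone would miss the end of the interval if Visit 8 took place after day 30. For a patient with no Visit 8 after the last dose, the 30-day limit would apply.

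The cost is a short protocol amendment and a few more adverse-event entries, mostly at a visit already scheduled. Reported event counts may rise slightly. The change concerns data recording only and alters no dosing or clinical management rule.
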